2.4 Secondary Endpoint (Group 2 only)

Standard wound healing techniques generally demonstrate 50% wound healing at 2 months. Therefore, the secondary endpoint for this study is the proportion of wound care patients that have at least 50% improvement in surface area within 2 months of treatment. This information will be used to describe if the study device is equivalent to standard and established techniques.

IRB# 1331496 Page 18 Version 6.0

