3.0 STUDY DESIGN

3.1 Study Design Overview

This study is a prospective, interventional, non-randomized, sequential phase study designed to assess the safety and efficacy of the Noxsano Bandage (study device) in subjects with a diabetic lower extremity ulceration and/or arterial insufficiency lower extremity ulceration.

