3.2 Subject Population and Sites

Group 1: Initial subjects will be limited to healthy volunteers with intact skin on their lower extremities. Five (5) white subjects and 5 black or African American subjects will be enrolled to evaluate skin differences. Group 1 (healthy volunteers without wounds) will have all follow-up completed and the results assessed before the investigators initiate prior to proceeding to Group 2 (wound care subjects).

Group 2: The subsequent wound care subject study will include 10 subjects from the patient population treated at the OhioHealth Riverside Methodist Hospital Critical Limb Care Center for lower extremity ulceration attributed to diabetes and/or arterial insufficiency.

[figure not shown]

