4.4 Inclusion Criteria

Group 1: Subjects must meet **all** of the following criteria to be eligible for enrollment:

- 1. Subject is \geq 18 and \leq 80 years of age.
- 2. Subject is white, black or African American
- 3. Subject has provided written informed consent.
- 4. Subject is willing to comply with study follow-up requirements.
- 5. Subject has intact skin on lower extremities.

Group 2: Subjects must meet **all** of the following criteria to be eligible for enrollment:

- 1. Subject is \geq 18 and \leq 80 years of age.
- 2. The wound to be treated with the Noxsano bandage has a baseline wound surface area of < 25 cm².
- 3. Subject has provided written informed consent.
- 4. Subject is willing to comply with study follow-up requirements.
- 5. Subject with at least **one** of the following:
 - a. Diabetic lower extremity ulceration with a hemoglobin A1c (HgbA1c) value ≤ 9.0, drawn within 3 months prior to study participation¹, and/or
 - b. Arterial insufficiency lower extremity ulceration with a post-revascularization ankle-brachial index (ABI) value of ≥ 0.40 and ≤ 0.80 on the involved extremity, performed within 3 months prior to study participation¹, and/or

IRB# 1331496 Page 21 Version 6.0

_

¹ Baseline measures of HgbA1c or ABI (within 3 months prior to consent) must be available for inclusion.

c. Diabetic and/or arterial insufficiency lower extremity ulceration deemed ineligible for revascularization with 3 months prior to study participation

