4.5 Exclusion Criteria

Group 1: Subjects will be excluded from the trial if **any** of the following criteria are met:

- 1. Subject is < 18 or ≥ 80 years of age.
- 2. Subject has a history of diabetes, arterial insufficiency, or osteomyelitis.
- 3. Subject has a known hypersensitivity to adhesives.
- 4. Subject is on any prescription medications, including contraceptives. Due to the short duration of the procedure period (3 days), subjects who initiate prescription medications during study participation will continue in the study.
- 5. Subject is pregnant, plans to become pregnant during the study period, or is breastfeeding.
- 6. Subject is non-English speaking or reading.
- 7. Subject is unable to give informed consent.

[figure not shown]
Group 2: Subjects will be excluded from the trial if **any** of the following criteria are met:

- 1. Subject is < 18 or ≥ 80 years of age.
- 2. The wound to be treated with the Noxsano bandage has a baseline wound surface area of ≥ 25 cm².
- 3. The wound to be treated with the Noxsano bandage is a plantar wound.
- 4. Subject with diabetes with an HgbA1c value of > 9.0, drawn within 3 months prior to study participation².
- 5. Subject with arterial insufficiency with an ABI value of < 0.40 or > 0.80, performed within 3 months prior to study participation³.
- 6. The wound to be treated with the Noxsano bandage has osteomyelitis contiguous with the treatment site.
- 7. Subject with peripherally-inserted central catheter (PICC) line antibiotic treatment within the previous 6 months.

IRB# 1331496 Page 22 Version 6.0

² Hemoglobin A1c is known to be significantly associated with wound healing rates, making it an important marker in the prediction of wound healing in diabetic patients [29]. A cutoff of 9.0% was chosen to exclude those with uncontrolled diabetes at highest risk for poor healing outcomes, as well as surgical complications including wound infections [30].

³ Patients with a normal-to-borderline ABI (> 0.80) are not characterized or diagnosed as having arterial insufficiency and are not referred to a vascular specialist; on the opposite end of the spectrum, those with severe arterial disease (< 0.40) typically proceed directly to hyperbaric treatment.

- 8. Subject requiring any type of amputation on the treatment limb within 3 months prior to study participation.
- 9. Subject with a known hypersensitivity to adhesives.
- 10. Subject is on active steroid therapy (does not include inhaled steroids).

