Group 2 (Wound Care Subjects): The initial device application visit (Day 0) may be combined with the screening/baseline visit. Group 2 subjects will be limited to a maximum wound surface area of $< 25 \text{ cm}^2$, to allow for complete coverage with the largest device size of $6 \times 8 \text{ cm}$. Those with wounds $\geq 25 \text{ cm}^2$, comprising less than 5% of the wound care population, will be excluded. Conversely, we are not limiting minimum wound size, as some of the most complicated wounds are actually under 1 cm^2 .

The standard wound measurement in centimeters using a conventional ruler will be obtained according the The OhioHealth Heart and Vascular Wound Care Center standard protocol prior to the initial device application at Day 0. The standard measurement per the current protocol at the Center for Critical Limb Care will be implemented and a photograph with the conventional ruler in place will be taken.

The study device will be applied to the lower extremity wound site by a trained investigator or sub-investigator. Routine wound care techniques such as debridement will be performed in the usual standard fashion prior to application of the Noxsano Bandage. The SAR questionnaire will be administered by study staff immediately following application of the Noxsano Bandage to assess tolerance, side effects, and/or adverse reactions (App. A).

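### A single unsourced figure of 50% at 2 months, with no control arm, cannot support a conclusion that the bandage is equivalent to standard care in the patients Group 2 enrols

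*Combined protocol and SAP*

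**What the plan says.** Section 3.1 describes the design: "This study is a prospective, interventional, non-randomized, sequential phase study". Section 3.2 gives the number of wound patients: "The subsequent wound care subject study will include 10 subjects from the patient population treated at the OhioHealth Riverside Methodist Hospital Critical Limb Care Center". No concurrent, matched or historical control group is described.

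Section 2.4 defines the secondary endpoint as "the proportion of wound care patients that have at least 50% improvement in surface area within 2 months of treatment". It justifies this with the statement that "Standard wound healing techniques generally demonstrate 50% wound healing at 2 months" and gives the purpose: "This information will be used to describe if the study device is equivalent to standard and established techniques". The protocol summary, 2.3 and 9.0 go further and say the study will determine equivalence. None of these places cites a source or names a population for the 50%.

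On who enters:
- Section 4.5, footnote 2, on HgbA1c: "A cutoff of 9.0% was chosen to exclude those with uncontrolled diabetes at highest risk for poor healing outcomes".
- Section 4.5, exclusion 5, removes arterial-insufficiency subjects with ABI below 0.40 or above 0.80.
- Section 4.5 also removes plantar wounds, contiguous osteomyelitis, recent PICC-line antibiotics, recent amputation on the treatment limb and active steroid therapy, without giving reasons.
- Section 4.4 admits diabetic ulcers (5a), arterial ulcers after revascularisation (5b) and, under 5c, "Diabetic and/or arterial insufficiency lower extremity ulceration deemed ineligible for revascularization".

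Section 9.0 plans mainly descriptive statistics. It has no stratification by ulcer type, no case-mix adjustment, no equivalence margin and no method for comparing Group 2 with the 50%.

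**The concern.** With no control arm, the 50% has to stand in for what the enrolled patients would have achieved on standard care. That works only if the figure comes from patients like them and measures the same quantity as the endpoint. The documents show neither.

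The protocol itself treats HgbA1c as a predictor of healing and filters on it, then applies a general figure to the filtered group. It pools ulcer types whose healing may differ and leaves their mix among 10 subjects to chance. Usual debridement continues under the bandage (5.7), so even an inert bandage would be expected to give roughly these patients' own standard-care result, whatever that is. At stake is a reported finding of equivalence, or of falling short of it, that reflects who enrolled.

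**Working it through.** **1. Can the 50% be reproduced?** No. The documents give no source, denominator, variance or population for it, and no derivation of n = 10.

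**2. What does the 50% measure?** Two readings are open.
- *Responder proportion:* half of standard-care patients reach the threshold. Then 50% is a benchmark for the endpoint.
- *Mean area reduction:* wounds shrink by half on average. Section 2.4 derives a per-patient area threshold from the figure, and 5.11 and 9.0 also use 50% as a per-patient threshold. On this reading no benchmark proportion exists, because a mean does not fix one. If every wound shrinks by exactly 50%, the mean is 50% and all patients are responders. If half close fully and half do not change, the mean is 0.5 × 100% + 0.5 × 0% = 50% and half are responders.

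**3. Which way does selection push?**

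| Feature | Reason given | Likely push on healing |
|---|---|---|
| HgbA1c > 9.0 excluded | Poor healing risk | Up |
| ABI < 0.40 excluded | Such patients go to hyperbaric treatment | Up |
| ABI > 0.80 excluded (arterial subjects) | Not regarded as arterial insufficiency | Down |
| Wounds of 25 cm² or more excluded, no minimum size | Device coverage; some of the most complicated wounds are under 1 cm² | Unclear |
| Non-revascularisable ulcers admitted (5c) | None | Down |
| Wounds described as non-healing (1.3.4) | Rationale only, no entry criterion | Down |

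The net direction cannot be read off this list.

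**4. What the gap contains.** Take the responder reading. Let p be the standard-care responder rate in the patients actually enrolled and d the device effect. The expected observed proportion is p + d, so

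gap from benchmark = d + (p − 0.50).

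The plan supplies no estimate of p, so d is not identified.

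**5. Illustration with d = 0.** The values of p are assumptions. For X responders among 10, P(X ≥ r) = Σ C(10,x) p^x (1 − p)^(10−x), summed over x from r to 10.

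| p | P(X ≥ 5) | P(X ≥ 7) | P(X ≤ 3) |
|---|---|---|---|
| 0.30 | 0.150 | 0.011 | 0.650 |
| 0.40 | 0.367 | 0.055 | 0.382 |
| 0.50 | 0.623 | 0.172 | 0.172 |
| 0.60 | 0.834 | 0.382 | 0.055 |
| 0.70 | 0.953 | 0.650 | 0.011 |
| 0.80 | 0.994 | 0.879 | 0.001 |

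An inert bandage can look good or bad against 50% according to p alone.

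**6. Case mix alone, under assumed rates.** With two ulcer types, the expected rate is (k/10)a + (1 − k/10)b.
- a = 0.55, b = 0.45: k = 8 gives 0.44 + 0.09 = 53%; k = 2 gives 0.11 + 0.36 = 47%. Shift 6 points.
- a = 0.60, b = 0.30: k = 8 gives 0.48 + 0.06 = 54%; k = 2 gives 0.12 + 0.24 = 36%. Shift 18 points.
- a = b: no shift.

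The documents contain no rates by ulcer type, so these show a mechanism, not a size.

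**7. Precision.** The exact (Clopper-Pearson) 95% interval for 5/10 solves P(X ≥ 5 | p) = 0.025 for the lower limit and P(X ≤ 5 | p) = 0.025 for the upper, giving 18.7% to 81.3%. For 7/10 it is 34.8% to 93.3%.

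**The case against.** The strongest defence is that little rests on the comparison. It is a secondary, descriptive endpoint in a first-in-human study of 10 wound patients, with no test against 50% and no decision rule. An interval of 18.7% to 81.3% is wider than any mismatch one could reasonably propose. This limits the seriousness of the point but does not remove it. The summary, 2.3 and 9.0 still say equivalence will be determined. An exact interval would show the imprecision but not that the benchmark may belong to other patients.

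A reader might infer that selection flatters the bandage by a calculable amount. If overall response is 50% and the criteria remove a fraction f who respond at rate r, the remaining rate is (0.50 − f × r)/(1 − f): 55% for f = 0.2 and r = 0.3, 67% for f = 0.3 and r = 0.1. The documents do not support this as an estimate. They give neither f nor r, and the calculation presumes the responder reading. The only exclusion frequency stated is for wounds of 25 cm² or more, "comprising less than 5% of the wound care population, will be excluded". A reader might also infer that the criteria as a whole were designed to remove poor healers. That reason is stated for HgbA1c only.

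The contrast between ulcer types may also be narrower than it looks, because exclusion 5 makes no exception for arterial-insufficiency subjects entering by 5c.

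**Conclusion.** The point holds. The plan offers an equivalence conclusion from one general, unsourced figure whose meaning is undefined and whose relevance to Group 2 is not shown. Following it could yield a statement about the bandage that is really about selection and case mix.

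The documents determine neither the direction nor the size of the mismatch. The probabilities and case-mix shifts above rest on assumed standard-care rates and on reading 50% as a responder proportion. On the mean-reduction reading the position is simpler: there is no benchmark proportion to compare with. The endpoint itself is sound as a descriptive measure; the inference drawn from it is what fails.

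**What to change.** In the protocol summary, 2.3, 2.4 and 9.0, remove the conclusion of equivalence with standard care. Keep the endpoint as defined in 2.4 and report it descriptively with an exact 95% interval, overall and listed by mutually exclusive ulcer type: diabetic only, arterial only, or both, with revascularised or ineligible status noted. Do not use 5a, 5b and 5c as strata. They are joined by and/or, so a diabetic ulcer ineligible for revascularisation can satisfy both 5a and 5c. With 10 subjects the breakdown should be a listing, without tests.

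If a comparison with 50% is kept, state what the figure measures and which population it comes from, and present it as context only. A reference drawn from the centre's own past patients who meet 4.4 and 4.5 would be better. It should be optional, because the documents do not show that past records hold the HgbA1c, ABI and revascularisation data it needs.

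The cost is wording, with no change to eligibility, treatment, visits or sample size. The study gives up an equivalence statement that its design cannot support.

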2.3 Secondary Objective (Group 2 only)

Group 2 (Efficacy): Wound Care Subjects. The secondary endpoint of the study is to determine if the study device is equivalent to standard and established techniques (standard techniques demonstrate 50% wound healing at 2 months) in subjects with active wounds.

[figure not shown]
IRB# 1331496 Page 17 Version 6.0

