5.10 Unscheduled Visits

A critical limb wound care podiatrist will be on call at all times.

Subjects will be instructed to call the Critical Limb Care Center [contact]) during regular business hours (0700-1600), and the Study Investigators will be available afterhours [contact] for [name], [contact] for [name], [contact] for [name]) for concerns regarding adverse reactions or other general questions. Subjects will be seen on an urgent basis as-needed based on podiatrist recommendation during regular business hours at the Critical Limb Care Center.

Unscheduled visits are additional visits that occur at times other than the protocol predetermined required visits during study participation. If an unscheduled visit occurs, the following will be collected from the subject's medical record and entered in the REDCap eCRF:

- ♦ Routine physical examination by a podiatrist, including assessment of the lower extremities
- ♦ Concomitant medications
- ♦ Photograph of the study device application site
- ♦ Wound Measurements
- ♦ Percent granulation tissue
- ♦ Bandage re-application if necessary
- ♦ SAR Questionnaire (App. A)

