- ♦ *Missed study follow-up visits:* Subjects who miss two consecutive follow-up visits will be contacted as described in section 5.12 in order to determine whether they wish to withdraw for the study or re-establish regular study follow-up visits. If subjects are able to re-establish study follow-up visits they may remain on the study. If the subject is unable to be contacted through the procedures outlined in section 5.12 data collection from the electronic medical record may continue, but the subject will be considered "lost to follow-up".
- ♦ Wound healing and discontinuation from study treatment: Clinical benefit may be determined during the treatment process by documentation of a healed ulceration, at which time the study device application will be discontinued. The post-treatment follow-up period will then begin for observation of late side effects and/or adverse reactions.
- ♦ *No evidence of wound healing at 2 months.* If a subject has no evidence of decreased wound surface area at 2 months (8 week treatment visit), the patient will be returned to standard and established techniques consistent with the wound etiology, and study follow-up will be discontinued.
- ♦ Wound < 50% healed at the completion of the study treatment period and discontinuation from study follow-up: If after 3 consecutive months (12 weeks) of treatment with the study device the wound does not exhibit at least a 50% decrease in surface area (cm²), the subject will be returned to standard and established techniques consistent with the wound etiology, and study follow-up will be discontinued. Clinical benefit experienced after the three-month treatment period, but not during the treatment period is not anticipated

In the absence of discontinuation due to adverse reactions (for both Groups 1 and 2) or wound healing outcomes (for Group 2 only) as indicated above, treatment may continue per the Schedule of Events (section 5.1) until one of the following criteria applies:

- ♦ Subject decision to withdraw from treatment (partial consent) or from the study (full consent),
- ♦ Death, or
- ♦ Funder reserves the right to temporarily suspend or prematurely discontinue this study.

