9.0 STATISTICAL CONSIDERATIONS

Primary Objective.

Group 1 (Safety): Healthy Volunteers. The initial phase of the study is designed to determine the safety of the study device in normal healthy volunteers without wounds. If there are no issues with tolerance, side effects, and/or adverse reactions in normal healthy volunteers, the second phase of the study will proceed with active wound care subjects.

Group 2 (Efficacy): Wound Care Subjects. The second phase of the study is designed to determine the effectiveness of the study device in wound healing in subjects with active wounds (see Primary Endpoint below), and to determine if the study device is equivalent to standard and established techniques (standard techniques demonstrate 50% wound healing at 2 months).

Primary Endpoint.

The primary endpoint for this study is wound healing (Group 2), as defined by the percent change in wound surface area (surface area is calculated in cm²) from baseline through the active treatment period. Wound care subjects will have the study device applied (and re-applied weekly) until the wound is judged to be healed by the wound care practitioner, for up to 3 months total duration. If after 2 consecutive months of treatment with the study device the wound does not exhibit at least 50% improvement in surface area (cm²), the subject will be returned to standard and established techniques consistent with the wound etiology. We will also determine if the study device is equivalent to standard and established techniques (standard techniques demonstrate 50% wound healing at 2 months).

Statistical Analysis Plan.

Descriptive statistics will comprise the bulk of the statistical analysis. Continuous variables will be reported as means and standard deviations, along with median and minimum/maximum values and compared between baseline and follow-up times using paired t-tests and/ or repeated measures ANOVA. Dichotomous and categorical variables will be reported as frequencies with percentages and compared between follow-up times using Chi-square tests or Kruskal Wallis tests. Imputation techniques will be used to account for missing data. Statistical significance will be set at p<0.05 for all the tests.

IRB# 1331496 Page 41 Version 6.0

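### Response is counted *within* 2 months but compared with a figure stated *at* 2 months; the reading that counts should be fixed at the 8-week visit

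*Combined protocol and SAP*

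**What the plan says.** Section 2.4 opens with the benchmark: "Standard wound healing techniques generally demonstrate 50% wound healing at 2 months". The next sentence defines the endpoint as "the proportion of wound care patients that have at least 50% improvement in surface area within 2 months of treatment". The section then states the purpose: "This information will be used to describe if the study device is equivalent to standard and established techniques". Section 2.3 repeats the benchmark in the same form: "standard techniques demonstrate 50% wound healing at 2 months". The protocol summary and section 9.0 also state it at 2 months.

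Area is calculated from ruler length and width (5.4). It is measured at every treatment visit: twice weekly for up to 4 weeks, then weekly (5.1, 5.8). The list for unscheduled visits in 5.10 also includes "Wound Measurements". No minimum wound size applies (5.7).

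A fixed 2-month reading does exist. The discontinuation rule in 5.11 refers to "no evidence of decreased wound surface area at 2 months (8 week treatment visit", which ties 2 months to the week-8 visit. The responder endpoint has no such tie. No section says whether the first, best, last or week-8 reading decides response, or whether a response must be confirmed. Section 9.0 specifies no analysis of this proportion.

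**The concern.** The two sides of the comparison are timed differently. The device side is a success if the threshold is reached at some point in an 8-week window with repeated readings. The benchmark side is worded as a value at the end of that window. A wound that reads a 52% reduction at week 5 and has regrown to a 20% reduction at week 8 is a responder under the plain wording of 2.4, but not on a week-8 reading. A single low ruler reading can have the same effect.

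There is no control arm to share this advantage, and section 2.4 makes this proportion its basis for describing equivalence to standard care. With 10 subjects (3.2: "The subsequent wound care subject study will include 10 subjects"), each reclassified subject moves the result by 10 percentage points.

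**Working it through.** The plan gives no sample-size, power or error-rate figure for this endpoint, so there is nothing to reproduce.

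**1. Number of readings by week 8 (5.1, 5.8).** Weeks 1–4: 4 × 2 = 8. Weeks 5–8: 4 × 1 = 4. Total about 12, or about 8 if the investigator allows weekly changes from the start. Unscheduled visits may add more.

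**2. Direction.** The week-8 reading is one of the readings in the window. If it shows at least a 50% reduction, so does at least one reading in the window. Hence the any-reading count is never below the week-8 count, whatever the healing pattern or error.

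**3. Model for size.** All inputs here are assumptions, because the documents give no repeatability figure and no healing variability.

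- True log area ratio at day t: L × t/56, with L normal, mean ln 0.5 (median reduction 50%) and SD 0.5 or 0.8.
- Observed log ratio: Y(t) = L × t/56 + e(t) − e(0). The errors e are normal with SD 0, 0.10 or 0.20 (CV about 0, 10, 20%), and every reading shares the baseline error e(0).
- Response: Y(t) ≤ ln 0.5.

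At week 8, Y(56) = L + e(56) − e(0) is symmetric about ln 0.5, so the responder proportion is 50% by construction. The any-reading proportion was simulated with 200,000 subjects per setting and 12 readings:

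| Area CV | Week 8 | Any reading, SD 0.5 | Any reading, SD 0.8 |
|---|---|---|---|
| 0% | 50% | 50% | 50% |
| 10% | 50% | 52% | 51% |
| 20% | 50% | 60% | 57% |

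In 10 subjects with SD 0.5, the excess is (0.52 − 0.50) × 10 = 0.2 to (0.60 − 0.50) × 10 = 1.0 subject.

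**4. Sensitivity.**

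- Errors correlated 0.5 across visits, baseline included: 51% (CV 10%) and 55% (CV 20%) with SD 0.5.
- 8 readings instead of 12: 52% and 59% with SD 0.5, so visit frequency barely matters.
- CV 30%: about 68% with SD 0.5 and 65% with SD 0.8. Adding true temporary fluctuation (SD 0.2 on the log scale) raises these to about 71% and 68%.
- True temporary fluctuation alone, without measurement error: 53–55%.

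**5. A single wound with a true 40% reduction at week 8 (a true non-responder), CV 20%.** At week 8 the chance of being called a responder is Φ[(ln 0.5 − ln 0.6)/(0.20 × √2)] = Φ(−0.1823/0.2828) = Φ(−0.645) = 26%. Under any reading it is 43% by simulation (42% with 8 readings). With error correlation 0.5 the pair is 18% and 27%.

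**6. Small wounds.** If the ruler is read to 0.1 cm (assumed), a wound of 0.5 × 0.5 = 0.25 cm² re-read as 0.4 × 0.3 = 0.12 cm² shows a reduction of 1 − 0.12/0.25 = 52%.

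**The case against.** The strongest reply is that 2.4 never says any, best or first reading. Its endpoint sentence follows on from a benchmark at 2 months, and elsewhere the plan applies area thresholds at fixed times: 5.11 at week 8, and 9.0 after 2 months for a 50% improvement. A week-8 reading may therefore be what was meant. That is possible, but 2.4 does not say it. The sentences in 5.11 and 9.0 govern continuation of treatment, not response, and they state different thresholds that need reconciling in their own right. If week 8 was intended, the same edit is needed.

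Second, a reader might infer that the device is shown to be flattered against standard care. The documents do not support that. The 50% figure has no source or definition and could be a mean area reduction, a share of responders or a share of healed wounds. Aligning the timing does not by itself make that comparison valid.

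Third, a reader might take the 26% versus 43% contrast as the inflation of the endpoint, or blame the dense visit schedule. The contrast describes one borderline non-responder; the endpoint is a proportion over mixed wounds and moves less. Early readings add almost nothing. One measurement protocol, trained staff and photograph review (5.4) also make partly shared error plausible, which shrinks the gap.

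Fourth, the comparison is descriptive with 10 subjects. Section 9.0 says "Statistical significance will be set at p<0.05 for all the tests" but specifies no test of this proportion against the benchmark, and 5 of 10 has an exact 95% interval of 19% to 81%. This stands and limits the consequence. It does not excuse a rule whose error runs in one direction only.

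**Conclusion.** The point holds as a timing mismatch with a known direction and an unknown, probably modest, size. Under the plain wording of 2.4 the responder count cannot be lower than at week 8 and may be higher. With independent error at CV 10–20%, steady healing, a median reduction of 50% and between-subject SD 0.5, the proportion rises from 50% to about 52–60% (51–57% with SD 0.8). Larger error or real fluctuation would widen the gap. Confidence is high on the wording and direction, and low on the exact size.

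**What to change.** In 2.4, with matching wording in 9.0:

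- Define response as a reduction of at least 50% in area from baseline at the 8-week treatment visit (± 2 days).
- Count a wound documented as healed before week 8 as a responder unless a reopening is recorded by then, and report these subjects separately. This rule is needed because device application stops at healing and the next scheduled visit is about 3 months later (5.9, 5.11), so these subjects may have no week-8 reading.
- Keep enrolled and treated subjects without a week-8 reading in the denominator as non-responders, including those removed after two consecutive missed visits and not replaced (5.11). Add a sensitivity analysis using the last available reading. With 10 subjects each such case moves the proportion by 10 points, and the general mention of imputation in 9.0 does not settle how they are handled.
- Report attainment at any time only as a descriptive extra, not against the 2-month benchmark.

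The cost is a few sentences. No visit or measurement is added. The downside is that the reported responder proportion may be slightly lower.
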